The primary efficacy endpoint for the original study was the 3-month change in Oswestry Disability Index (ODI) compared between the study arms. This comparison, as previously reported, found that at 3 months the per-protocol (PP) treatment group exhibited a 20.5 Least Squares Mean (LSM) improvement in ODI compared to a 15.2 LSM improvement in the sham group ( $p = 0.019$ ). The PP treatment arm subjects exhibited a durable ODI mean improvement (23.4 points) at 24 months. In terms of percent improvement in ODI from baseline, these results translate into mean percentage improvements of 46.2% at 12 months and 53.7% at 24 months. Responder rates for ODI and low back pain visual analogue scale (VAS) were also maintained through two years, with patients showing clinically meaningful improvements in both: ODI  $\geq$  10-point improvement in 76.4 percent of patients and ODI  $\geq$  20-point improvement in 57.5 percent; VAS  $\geq$  1.5 cm improvement in 70.2 percent of patients. Patients receiving the Intracept Procedure also decreased utilization of opioids and spinal injections as compared to utilization prior to treatment.

The purpose of this study is to measure the long term (5 + years) effectiveness outcomes in subjects treated with the Intracept Procedure in this original SMART study population.

 relevant medsystems	CD_3012_Rev B  Five-Plus Year Follow-Up of SMART Trial Statistical Analysis Plan	Date Effective: November 5, 2019  Page 6 of 21
--	---	---

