#### 4. STATISTICAL AND ANALYTICAL PLANS

##### 4.1 General Methodology

The SMART Five Plus Year Follow-up Study analysis will be performed when all US SMART treatment arm subjects have been approached to participate in the study, and all subjects who consented to participate, have completed their 5+ year follow-up study visit.

	CD_3012_Rev B Five-Plus Year Follow-Up of SMART Trial Statistical Analysis Plan	Date Effective: November 5, 2019 Page 9 of 21
---	---	---

The number of subjects in the analysis and reasons for withdrawal will be summarized in a CONSORT flowchart. All subjects consenting to participate in the long term follow-up study will be reported as observed. No imputations are planned for missing data.

All statistical processing will be performed by Technomics Research LLC. The standard operating procedures (SOPs) of Tehcnomics Research LLC will be followed in the creation and quality control of all data displays and analyses. Analyses will be conducted using SAS® software Version 9.3 or later unless otherwise stated.

Statistical tests will be two-sided and will be performed at the 0.05 level of significance.

Descriptive statistics will be used for secondary endpoints and will include the number and percentage of subjects in each category. For continuous parameters, descriptive statistics will include n (number of subjects), mean, SD, median, minimum, and maximum. Appropriate inferential statistics will be used for the primary and secondary efficacy variables.

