##### **4.4.3.3 Regression to the Mean**

Regression to the mean analyses for ODI and VAS will be performed as supplemental analyses. See Appendix A - Table 11.

 relevant medsystems	CD_3012_Rev B  Five-Plus Year Follow-Up of SMART Trial Statistical Analysis Plan	Date Effective: November 5, 2019  Page 11 of 21
---	---	--

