**5+ Year Follow-up Study Endpoints:**

Tables 8 and 9 will be performed for both the ITT (as treated) population and the Intracept treated only population.

Table 8 – Primary Endpoint Results	
	SMART 5+ Yr Follow-up Subjects N = XX Mean ± SD (N), Median [Interquartile Range], Range or % (n/N)
Time of Assessment	
Years since Index Procedure	Mean + SD, Median, Range
Percent with at Least 5 years of Follow-up	% (n/N)
ODI	(N=XX)
Baseline ODI Score (Mean + SD, Median, Range)	Mean + SD, Median, Range
5+ Year ODI Score (Mean + SD, Median, Range)	Mean + SD, Median, Range
Mean change in ODI score from baseline to 5+ Years post-treatment	Mean + SD, Median, Range ( p-value )
ODI Responder Rates	
Subjects with ≥ 10-point ODI decrease	% (n/N) ( p-value )
Subjects with ≥ 15-point ODI decrease	% (n/N) ( p-value )
Subjects with ≥ 20-point ODI decrease	% (n/N) ( p-value )
ODI Response Quartiles	
Subjects with ≤ 24% or less decrease	% (n/N)
Subjects with 25-49% decrease	% (n/N)
Subjects with 50-74% decrease	% (n/N)
Subjects with 75-100% decrease	% (n/N)
	(p-value)

	CD_3012_Rev B Five-Plus Year Follow-Up of SMART Trial Statistical Analysis Plan	Date Effective: November 5, 2019 Page 16 of 21
---	--	---

Table 9 – Secondary Endpoints Results	
	SMART 5+ Yr Follow-up Subjects N = XX
10 Point VAS Numeric Pain Scale	
Baseline VAS Score (Mean + SD, Median, Range)	Mean + SD, Median, Range
5+ Year VAS Score (Mean + SD, Median, Range)	Mean + SD, Median, Range
Mean change in VAS score from baseline to 3 months post-treatment	Mean + SD, Median, Range ( p-value )
VAS Responder Rates	
% of subjects with $\geq$ 1.5 Pt VAS decrease	% (n/N) ( p-value )
% of subjects with $\geq$ 2.0 Pt VAS decrease	% (n/N) ( p-value )
VAS Response Quartiles	
Subjects with $\leq$ 24% or less decrease	% (n/N)
Subjects with 25-49% decrease	% (n/N)
Subjects with 50-74% decrease	% (n/N)
Subjects with 75-100% decrease	% (n/N)
	( p-value )

Table 10 – Regression to the Mean Analysis	
	SMART 5+ Yr Follow-up Subjects N = XX
Regression to the Mean	
Average change in ODI in CONTROL group between baseline and 1 year	Mean, N, 95% CI, t-test p (Ho: $\delta=0$ )
Average change in ODI in CONTROL group between baseline and 2 years	Mean, N, 95% CI, t-test p (Ho: $\delta=0$ )

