Average change in ODI in INTRACEPT group between baseline and 1 year	Mean, N, 95% CI, t-test p (Ho: $\delta=0$ )
Average change in ODI in INTRACEPT group between baseline and 2 years	Mean, N, 95% CI, t-test p (Ho: $\delta=0$ )
Average change in ODI in INTRACEPT group between baseline and 5+ years	Mean, N, 95% CI, rm F-test p (Ho: $\delta=0$ )
Time (per year) effect on ODI in INTRACEPT group	Mean, N, 95% CI, rm F-test p (Ho: time=0)
Average change in VAS in CONTROL group between baseline and 1 year	Mean, N, 95% CI, t-test p (Ho: $\delta=0$ )
Average change in VAS in CONTROL group between baseline and 2 years	Mean, N, 95% CI, t-test p (Ho: $\delta=0$ )
Average change in VAS in INTRACEPT group between baseline and 1 year	Mean, N, 95% CI, t-test p (Ho: $\delta=0$ )
Average change in VAS in INTRACEPT group between baseline and 2 years	Mean, N, 95% CI, t-test p (Ho: $\delta=0$ )
Average change in VAS in INTRACEPT group between baseline and 5+ years	Mean, N, 95% CI, t-test p (Ho: $\delta=0$ )
Time (per year) effect on VAS in INTRACEPT group	Mean, N, 95% CI, rm F-test p (Ho: time=0)

	CD_3012_Rev B Five-Plus Year Follow-Up of SMART Trial Statistical Analysis Plan	Date Effective: November 5, 2019 Page 17 of 21
---	--	---

Table 11 – Comparison of SMART Endpoints			
Characteristic	SMART Treated Subjects in 5+ Yr Follow-up N = XX	SMART Treated Subjects Not in 5+ Year Follow-up N = XX	t-test of Means or Exact Test of Proportions
Change in ODI (Baseline to 3 Months)	Mean + SD, Median, Range	Mean + SD, Median, Range	
Change in VAS (Baseline to 3 Months)	Mean + SD, Median, Range	Mean + SD, Median, Range	
ODI Responders ( $\geq$ point ODI reduction)	% (n/N)	% (n/N)	

Table 12 – Opioids & Injections Utilization	
SMART 5+ Yr Follow-up Subjects N = XX	
Opioid Use	
Subjects Taking Opioids at Baseline	% (n/N)
Subjects actively taking Opioids in last 30 days (5+ Year Follow-up Visit)	% (n/N)
Opioid Dosage (in subjects taking opioids)	
Opioid Dosage at Baseline	Mean + SD, Median, Range
Opioid Dosage at 5+ years post treatment	Mean + SD, Median, Range
Epidural Injections	
Subjects with prior injections at baseline	Mean + SD, Median, Range
Subjects with injections in 12 months prior to 5+ year post treatment visit	Mean + SD, Median, Range
Subjects with injections for low back pain treatment in the same location as Intracept treatment (in the past 12 months):	Mean + SD, Median, Range

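### SAP Table 10, the regression-to-the-mean analysis, tests each arm's change against zero and has no Intracept-minus-Control contrast, so its p-values cannot separate regression to the mean from a treatment effect

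*SAP*

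**What the plan says.** SAP 4.4.3.3 says only that "Regression to the mean analyses for ODI and VAS will be performed as supplemental analyses". It gives no model, contrast or decision rule. It points to Table 11, but the analysis is in Table 10.

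Table 10 has twelve rows:

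- **Four Control rows:** ODI and VAS change at 1 and 2 years, for example "Average change in ODI in CONTROL group between baseline and 1 year" and "Average change in ODI in CONTROL group between baseline and 2 years".
- **Six Intracept change rows:** ODI and VAS change at 1, 2 and 5+ years, for example "Average change in ODI in INTRACEPT group between baseline and 2 years".
- **Two Intracept time rows:** a per-year effect on ODI and on VAS, reported as "Mean, N, 95% CI, rm F-test p (Ho: time=0").

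Each of the ten change rows reports a mean, N, 95% CI and a p-value for the null that this arm's mean change is zero. The test is a t-test in nine rows and a repeated-measures F-test for ODI at 5+ years. SAP 4.1 sets the level: "Statistical tests will be two-sided and will be performed at the 0.05 level of significance".

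The SAP Introduction reports the 3-month ODI result of the randomised trial: a 20.5-point improvement in the per-protocol Intracept group "compared to a 15.2 LSM improvement in the sham group", with p = 0.019.

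**The concern.** The follow-up study has one arm, and its primary endpoint is change from baseline. Regression to the mean is a main rival explanation for such a change, and Table 10 is the only planned analysis named for it. The question is whether the Intracept change exceeds what would be expected without ablation. A test of zero change asks something else. Regression to the mean makes that null false just as a treatment effect does, so a small p-value is compatible with either.

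Randomisation supplies the right comparison. Regression to the mean is expected to be equal in the two arms, so the difference in change cancels it. Table 10 already needs both arms' data at 1 and 2 years but omits that difference. If one arm's row were significant and the other's not, reading this as a difference between arms would be a further error. What is at stake is that a table with this title, filled with small p-values, could be taken to have excluded an explanation that those p-values do not test.

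**Working it through.** **Inputs from the documents.** Two-sided alpha 0.05 (SAP 4.1). Sham ODI change 15.2 and Intracept 20.5 at 3 months, p = 0.019 (SAP Introduction). At most 133 Intracept subjects (SAP 2.1). 202 US subjects enrolled, so Control n is about 202 − 133 = 69. The documents give no SD of ODI change and no sham change at 1 or 2 years.

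**Step 1. A plausible SD.** The plan states no figure for Table 10 to reproduce, and p = 0.019 cannot be reproduced without an SD and the per-protocol arm sizes. It can be inverted:

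- Difference = 20.5 − 15.2 = 5.3.
- SE = 5.3 / z(1 − 0.019/2) = 5.3 / 2.346 = 2.26.
- SD = SE / sqrt(1/n_T + 1/n_C) = 14.3 for assumed arms of 120:60, and 16.0 for 150:75.

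The ranges below use SD 15 to 25 to allow for more spread.

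**Step 2. Intracept ODI change rows if Intracept only matched sham.** t = d / (SD / sqrt(n)). Rejection probabilities come from the noncentral t distribution.

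- d = 15.2, SD 16: t = 15.2 / (16 / sqrt(133)) = 11.0 at n = 133, and 6.7 at n = 50.
- d = 15.2, SD 25, n = 50 (least favourable case): t = 15.2 / (25 / sqrt(50)) = 4.3, rejection probability 98.8%.

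**Step 3. Smaller changes**, because 15.2 may overstate pure regression to the mean.

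| True change in both arms | SD | n | Probability Intracept row p < 0.05 |
|---|---|---|---|
| 8 | 22 | 60 | 79% |
| 8 | 15 | 133 | about 100% |
| 5 | 22 | 60 | 41% |
| 5 | 15 | 133 | 97% |
| 3 | 16 | 50 | 26% |
| 3 | 16 | 133 | 57% |

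At SD 16 the smallest observed change reaching p < 0.05 is t(0.975, n − 1) × 16 / sqrt(n) = 2.7 points at n = 133 and 4.5 at n = 50. SAP 2.5 gives 10 points as the minimally important difference.

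**Step 4. The between-arm contrast.** With equal true change in the two arms, a direct two-sample test rejected in 4.5% to 5.6% of 5,000 simulated trials per setting (d = 5, 8 and 15.2; SD 15 to 22; n 60 to 133 against 69). Its 95% CI half-width is 1.96 × SD × sqrt(1/n + 1/69):

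- SD 15, n = 133: 4.4 points.
- SD 22, n = 60: 7.6 points.

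If the true gap were 5.3 points, power at 133:69 and SD 16 would be about 61%.

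**Step 5. The time rows.** In 2,000 simulated runs with a sustained 15.2-point drop (SD 16, assumed within-subject correlation 0.3), the slope test rejected in about 100% when baseline was in the model. It rejected in 4.8% to 5.6% when only post-baseline visits were fitted. The SAP does not say which model applies.

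**The case against.** **The analysis is supplemental and has no decision rule.** True. The only conclusion tied to p ≤ 0.05 is in SAP 4.4.2 and concerns the primary analysis. That Table 10 would be cited as excluding regression to the mean is a risk, not something the SAP states. This limits the weight of the point but leaves the null wrong for the table's purpose.

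**The needed figures are mostly printed already.** Table 10 gives mean, N and 95% CI for both arms at 1 and 2 years, so a reader can compare the arms informally and derive an unadjusted difference. This stands. It is the p-values that are uninformative, and the comparison is left to the reader. At 5+ years there is no Control row to compare with.

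**The 15.2 points is a stand-in.** It is a 3-month figure that mixes regression to the mean, sham response and natural course. The primary inclusion requirements listed in the SAP Introduction name no ODI or VAS threshold, so the size of regression to the mean cannot be derived from the documents. This also stands, and is why Step 3 covers smaller changes.

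**A stronger reading does not hold.** A reader might infer that every Intracept row in Table 10 would be significant even if Intracept did no better than sham. The documents do not support that. Two of the eight Intracept rows test a time slope, which may reject at only about 5%. No sham VAS change is given, so the three VAS change rows have no derivable rejection rate. At a true change of 3 to 5 points the ODI rows are not certain to be significant.

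**Conclusion.** The concern holds for the ten change rows. Their null is one that regression to the mean itself breaks, and Table 10 has no between-arm contrast, so its p-values cannot answer the question in its title. For ODI, if Intracept only matched a 15.2-point change, the Intracept change rows would be significant almost surely: about 98.8% or more for SD up to 25 and n of at least 50. At 5 points the figure is about 41% to 97% (SD 15 to 22, n 60 to 133). The nominal rate is 5%, and a direct comparison of the arms keeps to it.

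These sizes rest on assumed SDs, an unknown number seen at 5+ years, and assumed sham changes. For VAS only the logic carries over. The defect is in a supplemental table: it does not alter the primary test, and it does not show that the Intracept change is due to regression to the mean.

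**What to change.** In Table 10 and SAP 4.4.3.3:

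1. Keep each arm's mean, N and 95% CI as description, and remove the zero-change p-values.
2. Add rows for the Intracept-minus-Control difference in ODI change and VAS change at 1 and 2 years, with 95% CI, from an ANCOVA with arm and baseline score. Base any statement about regression to the mean on these rows.
3. If any Control subjects received the procedure before a visit (the documents do not say), flag this and limit the contrast to visits before it.
4. For 5+ years, state that the change row cannot exclude regression to the mean. Do not add a test that carries an earlier Control change forward. Its interval would ignore the extrapolation, the self-selection of 5+ year participants and the move to a telephone integer pain rating.
5. Say whether the time model includes baseline, and correct the pointer from Table 11 to Table 10. Also say which subjects fill each row, because the column header names 5+ year subjects while four rows are Control.

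**Cost.** The change edits the SAP text and a table shell, using data that Table 10 already needs. No new patients or visits are required. The between-arm interval is wider, with a half-width of about 4.4 to 7.6 ODI points at best, assuming no Control attrition. The result will be less favourable than a test against zero. The contrast also removes sham response and natural course, so it is stricter than a correction for regression to the mean alone.

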#### **4.2 Baseline Definition**

Intra-subject comparisons of baseline to 5+ years post procedure will be made unless otherwise stated. Baseline is defined as the last non-missing assessment at or before the baseline visit and prior to Intracept treatment.

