Modic II	% (n/N)	% (n/N)	
L4 Superior Endplate	% (n/N)	% (n/N)	
Modic I	% (n/N)	% (n/N)	
Modic II	% (n/N)	% (n/N)	
L4 Inferior Endplate	% (n/N)	% (n/N)	
Modic I	% (n/N)	% (n/N)	
Modic II	% (n/N)	% (n/N)	
L5 Superior Endplate	% (n/N)	% (n/N)	
Modic I	% (n/N)	% (n/N)	
Modic II	% (n/N)	% (n/N)	
L5 Inferior Endplate	% (n/N)	% (n/N)	
Modic I	% (n/N)	% (n/N)	
Modic II	% (n/N)	% (n/N)	
S1 Superior Endplate	% (n/N)	% (n/N)	
Modic I	% (n/N)	% (n/N)	
Modic II	% (n/N)	% (n/N)	

relevant medsystems	CD_3012_Rev B  Five-Plus Year Follow-Up of SMART Trial Statistical Analysis Plan	Date Effective: November 5, 2019  Page 14 of 21
-------------------------------	---	--

Table 6 – Baseline Low Back Treatment History			
Characteristic	SMART Treated Subjects in 5+ Yr Follow-up N = XX	SMART Treated Subjects Not in 5+ Year Follow-up N = XX	t-test of Means or Exact Test of Proportions
Medications			
Opioid Medications	% (n/N)	% (n/N)	
Total Opioid Equianalgesic Average Daily Dose in 7 days prior to Baseline	Mean + SD, Median, Range	Mean + SD, Median, Range	
Injections	% (n/N)	% (n/N)	
Epidural Injections	% (n/N)	% (n/N)	
Facet Injections	% (n/N)	% (n/N)	
Other Injections	% (n/N)	% (n/N)	

Table 7 – RF Ablation Table			
Characteristic	SMART Treated Subjects in 5+ Yr Follow-up N = XX	SMART Treated Subjects Not in 5+ Year Follow-up N = XX	t-test of Means or Exact Test of Proportions
VB Treated			
L3	% (n/N)	% (n/N)	
L4	% (n/N)	% (n/N)	
L5	% (n/N)	% (n/N)	
SI	% (n/N)	% (n/N)	

	CD_3012_Rev B Five-Plus Year Follow-Up of SMART Trial Statistical Analysis Plan	Date Effective: November 5, 2019 Page 15 of 21
---	--	---

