Mean # of injections per subject in 12 months prior to baseline	% (n/N)
Mean # of injections per subject in 12 months prior to 5+ year post treatment visit	% (n/N)
Time to first injection for low back pain in same location post Intracept Procedure	Mean + SD, Median, Range

	CD_3012_Rev B Five-Plus Year Follow-Up of SMART Trial Statistical Analysis Plan	Date Effective: November 5, 2019 Page 18 of 21
---	--	---

Table 13 – Surgical Interventions	
	SMART 5+ Yr Follow-up Subjects N = XX
Number (%) of subject reporting a procedure	% (n/N)
Number of procedures	% (n/N)
Re-intervention Rate over Time	
1 Year	S% (95% CI)
2 Year	S% (95% CI)
5 Year	S% (95% CI)
Type of procedure:	
Discectomy	% (n/N)
Lumbar fusion	% (n/N)
RF Ablation	% (n/N)
Other	% (n/N)
At the same level of Intracept treatment?	
Yes	% (n/N)
No	% (n/N)
Time to intervention (post Intracept procedure)	Mean + SD, Median, Range
Same etiology and level as Intracept treatment	Mean + SD, Median, Range
Different etiology or level from Intracept treatment	Mean + SD, Median, Range

Table 14 – Pain Status at 5 + Years	
	SMART 5+ Yr Follow-up Subjects N = XX
Pain Status	
Constant	% (n/N)
Intermittent	% (n/N)
No Pain	% (n/N)
Experiencing Pain	
Same location as prior to Intracept Procedure	% (n/N)
Different location from prior to Intracept Procedure	% (n/N)
Same nature as prior to Intracept Procedure	% (n/N)
Different nature from prior to Intracept Procedure	% (n/N)
Time (per year) effect on VAS in INTRACEPT group	Mean, N, 95% CI, rm F-test p (Ho: time=0)

	CD_3012_Rev B Five-Plus Year Follow-Up of SMART Trial Statistical Analysis Plan	Date Effective: November 5, 2019 Page 19 of 21
---	--	---

Table 15 – Durability at 5 + Years	
	SMART 5+ Yr Follow-up Subjects N = XX
Number (%) of subjects reporting a re-intervention (lumbar procedure adjudicated as same location and etiology as Intracept procedure)	% (n/N)
Number (%) of subjects reporting actively using opioids (defined as > 25% of total prescribed dosage in 30 days prior to visit)	%(n/N)
Number (%) of subjects reporting low back pain injections in same treatment location as Intracept.	% (n/N)
Number (%) of subjects reporting less than 2 point decrease in pain (in same location) compared to baseline	% (n/N)
Number (%) of subjects reporting less than 10 point decrease in ODI compared to baseline	% (n/N)

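### SAP Table 12 reports opioid dose only among takers, so its baseline and 5+ year means probably describe different people and can move opposite to actual intake

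*SAP*

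**What the plan says.** SAP Appendix A, Table 12 begins with two counts, "Subjects Taking Opioids at Baseline" and "Subjects actively taking Opioids in last 30 days (5+ Year Follow-up Visit", each as a percentage with n/N. Below them, under "Opioid Dosage (in subjects taking opioids", stand two rows, "Opioid Dosage at Baseline" and "Opioid Dosage at 5+ years post treatment". Each is summarised by mean, SD, median and range. The table has no row for within-subject change, no row that counts non-takers as zero, no breakdown of who stopped or started, and no dose unit.

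Other places bear on this:

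- SAP 4.2 sets a default: "Intra-subject comparisons of baseline to 5+ years post procedure will be made unless otherwise stated".
- SAP Table 6 plans a baseline summary with a unit and a window, "Total Opioid Equianalgesic Average Daily Dose in 7 days prior to Baseline", and no restriction to takers.
- Protocol 7.4 has drug type, prescribed dosage and average daily dose over the last 30 days recorded at the 5+ year visit.
- SAP 3.1.2 and Table 15 define active use as more than 25% of the dosage in the 30 days before the visit. The Table 15 row begins "Number (%) of subjects reporting actively using opioids (defined as".
- The listed opioid endpoint (protocol 5.2, SAP 3.1.2) is a proportion of users. Dose is not an endpoint.

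**The concern.** Whether a subject takes opioids at 5+ years is itself an outcome after treatment. If the second dosage row is restricted to takers at that visit, it is conditioned on that outcome. A subject who stopped drops out of the row instead of contributing a zero, and a subject who started appears only in the second row. The difference between the two means is then not a change in anyone's dose.

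This is the SAP's only before-and-after display of opioid dose. Both documents' introductions cite lower opioid utilization after treatment than before it, so two dose means side by side are likely to be read as a change.

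**Working it through.** **No plan figure to reproduce.** The documents give no opioid doses or user counts. The inputs below are assumptions that show what can happen.

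**Which set the heading means.** The words do not say whether takers are identified at each visit. The two rows directly above count takers separately at baseline and at 5+ years, so by-visit is the natural reading. The alternative is one set of baseline takers followed over time.

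**Formulas.**

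- Takers-only mean at a visit: m = (sum of doses) / (takers at that visit).
- All-subject mean: M = (sum of doses) / N, with non-takers at 0.
- Hence M = p × m, where p is the proportion taking. The takers-only mean rises while intake falls whenever 1 < m₁/m₀ < p₀/p₁.

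**Assumed cohort.** N = 100 followed. At baseline 40 take opioids, 20 at 10 units/day and 20 at 60 units/day. The sum is 200 + 1200 = 1400, so m = 1400/40 = 35.0 and M = 1400/100 = 14.0.

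| Scenario | Sum at 5+ years | Takers | Takers-only mean (from 35.0) | All-subject mean (from 14.0) |
|---|---|---|---|---|
| A: 18 low-dose takers stop | 2×10 + 20×60 = 1220 | 22 | 55.5 (up) | 12.2 (down) |
| A2: as A, and the rest cut dose by 10% | 0.9×1220 = 1098 | 22 | 49.9 (up) | 11.0 (down) |
| B: 20 start at 10, nobody stops | 1400 + 200 = 1600 | 60 | 26.7 (down) | 16.0 (up) |
| C: 10 of each dose group stop | 100 + 600 = 700 | 20 | 35.0 (flat) | 7.0 (halved) |

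In A, m₁/m₀ = 55.5/35.0 = 1.58 and p₀/p₁ = 0.40/0.22 = 1.82, so the condition is met. In A2 every baseline taker either stopped or reduced, yet the takers-only mean rises.

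**Sensitivity to the number who move.** With 4, 8, 12, 16 or 20 of the 20 low-dose takers stopping, the takers-only mean rises to 37.8, 41.2, 45.7, 51.7 or 60.0, while intake falls to 13.6, 13.2, 12.8, 12.4 or 12.0. With 5, 10 or 30 low-dose starters and no stoppers, the takers-only mean falls to 32.2, 30.0 or 24.3, while intake rises to 14.5, 15.0 or 17.0.

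**The alternative reading.** If the 40 baseline takers are followed with stoppers at 0, scenario A gives 1220/40 = 30.5, the right direction. Scenario B then gives 1400/40 = 35.0, unchanged, because the starters are missed.

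**Can the printed percentages repair it?** In A, 40% × 35.0 = 14.0 and 22% × 55.5 = 12.2, so yes, if both rows count the same takers. Now assume 22 takers at 5+ years, of whom 16 are active at 60 and 6 are below the 25% threshold at 8. The sum is 960 + 48 = 1008, so true intake is 10.1. The any-taker mean is 1008/22 = 45.8, and the active percentage times that mean is 0.16 × 45.8 = 7.3.

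**The case against.** The strongest reply is that Table 12 already gives a usual two-part description of a variable with many zeros: the percentage taking, then the dose among takers. A reader who multiplies adjacent cells recovers mean intake in scenarios A and B and sees the right direction. This largely stands. It fails where the two rows count different takers, and the wording allows that at 5+ years (*actively taking* against *taking*). It also cannot yield a within-subject change, its interval, or the numbers who stopped and started.

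Second, dose is not an endpoint. The dosage rows carry no p-value or change row, whereas Tables 8 and 9 give a mean change with a p-value for ODI and pain. This stands and limits the importance of the point.

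Third, the scenarios are constructed. This also stands. With continuing takers' doses held fixed, opposite movement needs stopping or starting to be related to dose. Scenario C shows only a flat mean.

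Fourth, Table 6 already names the unit, so its absence from Table 12 is a labelling gap. That is fair, although protocol 7.4 collects both prescribed dosage and average daily dose, and Table 12 does not say which it summarises.

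A reader might infer that the SAP expressly defines takers visit by visit in conflict with 4.2. It does not: the by-visit reading is an inference, and 4.2 allows exceptions where stated.

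**Conclusion.** The point holds as a weakness in a descriptive table. On its natural reading, Table 12 compares mean doses in two different groups, the second selected on a post-treatment outcome. The difference can have the opposite sign to the change in intake when stopping or starting is related to dose. In the assumed cohort the takers-only mean moves up to 25 units/day (35.0 to 60.0) while intake moves by 2.0 the other way (14.0 to 12.0). Those sizes rest wholly on assumed doses and counts. They show that reversal is possible, not that it is likely here.

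Two stronger conclusions might be drawn, and the documents support neither. One is that the table will misstate the direction of opioid use: the percentage rows largely guard against that, and nothing in the documents shows how stopping relates to dose. The other is that the opioid endpoint, the composite or the primary result is affected: the endpoint and the composite use active use, not dose, and the primary analysis concerns ODI.

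**What to change.** In the Table 12 shell:

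- Keep the users-only dosage rows, labelled as not comparable over time, with n in each row and one stated definition of *taking* shared with the percentage rows.
- Add average daily equianalgesic dose (the Table 6 unit) in all 5+ year attendees with both assessments, entering confirmed non-users as 0. Show baseline, 5+ years and the paired change with its 95% CI and median. A confirmed non-user's 0 is an observed value, so it respects the no-imputation rule. An unknown dose stays missing.
- Add counts of subjects who stopped, continued and started.
- Footnote that the baseline dose covers 7 days (Table 6) and the 5+ year dose 30 days (protocol 7.4).

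The cost is a revised shell and a small amount of programming. No new data are needed, because protocol 7.4 collects drug type and average daily dose and Table 6 already plans the baseline equianalgesic dose. The downside is that the paired change remains approximate because the two windows differ.
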